# 4.2 RANDOMIZATION

In this non blinded study, randomization will be used to avoid bias in the assignment of the stapling device to be utilized for RA/RV transection for each subject, to increase the likelihood that attributes of the subject are evenly balanced between groups, and to enhance the validity of statistical comparisons between groups.

The Sponsor will assign the stapling device randomly to each subject on a 1:1 basis to either the surgeon's current SOC or PVS.

In the event that a potential subject fails inclusion/exclusion criteria prior to randomization, this subject will be considered a screen failure.

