# 4.7.4 Visit 3 – Postoperative through Discharge

Post procedure assessments will be completed from OR discharge until hospital discharge. Data to be collected includes:

• Post-operative interventions/procedures related to RA/RV bleeding, if applicable:

- Hemostasis intervention: bleeding that occurs post-operatively requiring blood or blood product transfusion or an additional surgical procedure (and the relationship to SOC/PVS for RA/RV transection);
- Date of drain removal, if applicable
- Daily volume and characteristics of drainage (drain);
- Concomitant procedures/ interventions performed, if applicable;
- Adverse Events;
- Concomitant medication (associated with AEs); and
- Discharge date

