# 7.6 ANALYSIS OF SAFETY

The number and percentage of subjects requiring hemostasis interventions postoperatively that are classified as related to SOC/PVS for RA/RV transection (e.g. need for blood product transfusion or additional surgical procedure) will be summarized for each

group as a primary safety endpoint.

Safety will be assessed through the incidence of AEs and serious adverse events (SAEs), which will be coded using the Medical Dictionary for Regulatory Activities (MedDRA). The incidence of AEs will be summarized at the MedDRA system organ class and preferred term level. Incidence of AEs will also be summarized by maximum severity. All reported adverse events will be listed.

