1.2 Study Design

This was a prospective, randomized, controlled, multi-center, open-label study that planned to collect and compare data from the surgeon's current SOC stapler (for RA/RV transection) and PVS. Prospective subjects were informed about the nature of the research, given the informed consent document (ICD) to read, and if the subject understood the consent, were asked to provide written consent.

2 Treatment Assignment

Subjects were assigned to either the surgeon's current SOC stapler or PVS. The ECHELON FLEX™ PVS with Advanced Placement Tip is a sterile, single use instrument that simultaneously cuts and staples tissue. There are four staggered rows of staples, two on either side of the cut line. The ECHELON FLEX™ PVS with Advanced Placement Tip and reloads have a staple line that is approximately 35 mm long and a cut line that is approximately 30 mm long. The shaft can rotate freely in both directions and an articulation mechanism enables the distal portion of the shaft to pivot to facilitate lateral access to the operative site. The powered vascular stapler has been cleared for marketing by the FDA and is CE marked which allows for commercial distribution in the European Union. The device was used in accordance with its product labeling and Instructions for Use.

3 Randomization and Blinding Procedures

Subjects were randomized to either the surgeon's current SOC stapler or PVS in a 1:1 ratio. Randomization could have occurred at any time prior to surgery up to transection of the vessel(s). Sites were instructed to wait until as close as possible to the actual time of vessel transection so as to minimize randomized drops within the study.

Randomization was accomplished through utilization of envelopes at the study site. Randomization envelopes were created according to the “Work Instructions for the Creation of Randomization Envelopes”, document number WE001625, based on a randomization schedule generated by the Ethicon Biostatistics group. The randomization schedule was generated using a validated program that incorporated variable block sizes, and treatment assignment was balanced within each study site. This was an open-label study and therefore no blinding procedures were required.

4 Interval Windows

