5.2 Primary Safety Endpoint

The primary safety endpoint was defined as the occurrence of hemostatic interventions/procedures completed for post-operative bleeding related to the transection of the RA and RV with the use of SOC or PVS. Hemostasis intervention was defined as bleeding that occurred post-operatively requiring blood or blood product transfusion or an additional surgical procedure (related to RA and RV transection). No hemostasis intervention was defined as no interventions needed for post-operative bleeding (related to RA and RV transection). This endpoint was recorded at the subject level as it was based on post-operative interventions and not specific to any individual firing.

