10.11 Safety Analyses

Safety will be assessed through the incidence of adverse events (AEs) and serious adverse events (SAEs), which will be coded using the Medical Dictionary for Regulatory Activities (MedDRA). The number and percentage of subjects reporting AEs and SAEs will be summarized at the MedDRA system organ class and preferred term level by treatment group and overall. Similar summaries will also be provided for AEs and SAEs related to the study device, as well as for AEs and SAEs related to the study procedure. Related events are those where the relationship is indicated as Possibly, Related, or Unknown. The incidence of AEs will also be summarized by maximum severity. All reported adverse events will be listed.

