Two-sided 95% Confidence Interval for Percent Difference (One-sided 95% CI Upper Limit) for Percent Requiring Transection [2]	xx.x%, xx.x%	xx.x%, xx.x%	xx.x%, xx.x%
	xx.x% (xx.x%)		
Type of Intervention, n (%) [3]			
Additional Stapling	xx (xx.x%)	xx (xx.x%)	xx (xx.x%)
Over-sewing	xx (xx.x%)	xx (xx.x%)	xx (xx.x%)
Compression	xx (xx.x%)	xx (xx.x%)	xx (xx.x%)
Use of Suture	xx (xx.x%)	xx (xx.x%)	xx (xx.x%)
Sealant	xx (xx.x%)	xx (xx.x%)	xx (xx.x%)
Buttress	xx (xx.x%)	xx (xx.x%)	xx (xx.x%)
Use of Energy	xx (xx.x%)	xx (xx.x%)	xx (xx.x%)
Clip Placement	xx (xx.x%)	xx (xx.x%)	xx (xx.x%)
Blood Product Transfusion	xx (xx.x%)	xx (xx.x%)	xx (xx.x%)
Additional Surgical Procedure	xx (xx.x%)	xx (xx.x%)	xx (xx.x%)
Other Intervention	xx (xx.x%)	xx (xx.x%)	xx (xx.x%)
Intervention Category, n (%) [4]			
No Intervention	xx (xx.x%)	xx (xx.x%)	xx (xx.x%)
Hemostasis Controllable	xx (xx.x%)	xx (xx.x%)	xx (xx.x%)
Hemostasis Intervention	xx (xx.x%)	xx (xx.x%)	xx (xx.x%)

[1] Denominator for calculation of percentage is the total number of vessels transected in that group.

[2] Difference is calculated as Powered Vascular Stapler minus Standard of Care Stapler.

[3] Denominator for calculation of percentage is the total number of vessels requiring intervention in that group.

[4] Hemostasis Controllable includes additional stapling, over-sewing, compression, use of suture, sealant, buttress, use of energy, clip placement, or other intervention.
 Hemostasis Intervention includes blood product transfusion and additional surgical procedure.

Table 7
 Post-Operative Interventions or Procedures Related to Renal Artery or Renal Vein Bleeding
 Safety Set

Characteristics	Standard of Care Stapler (N = ##)	Powered Vascular Stapler (N = ##)	Overall (N = ##)
Number of Subjects Requiring Post-Operative Intervention Related to Renal Artery or Renal Vein Bleeding			
n (%) [1]	xx (xx.x%)	xx (xx.x%)	xx (xx.x%)
95% Confidence Interval for Percent	xx.x%, xx.x%	xx.x%, xx.x%	xx.x%, xx.x%
Type of Intervention, n (%) [2]			
Blood Product Transfusion	xx (xx.x%)	xx (xx.x%)	xx (xx.x%)
Additional Surgical Procedure	xx (xx.x%)	xx (xx.x%)	xx (xx.x%)
Other Intervention	xx (xx.x%)	xx (xx.x%)	xx (xx.x%)

[1] Denominator for calculation of percentage is the total number of subjects in that group.
 [2] Denominator for calculation of percentage is the total number of subjects requiring intervention in that group.

Table 8
 Device Usage Details
 Full Analysis Set

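### The primary safety endpoint counts only post-operative bleeding interventions attributed to the renal-vessel transection in an open-label study, and no planned table compares the arms without that condition

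*Protocol*

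**What the plan says.** The relatedness condition appears in every definition of the endpoint, in differing words:

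- Protocol 7.6 summarises "The number and percentage of subjects requiring hemostasis interventions postoperatively that are classified as related to SOC/PVS for RA/RV transection". Protocol 3.2 carries a similar restriction.
- SAP 5.2 counts "bleeding that occurred post-operatively requiring blood or blood product transfusion or an additional surgical procedure (related to RA and RV transection" and records the endpoint once per subject.
- The Table 7 shell labels its row "Number of Subjects Requiring Post-Operative Intervention Related to Renal Artery or Renal Vein Bleeding".

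Protocol 4.7.4 (Visit 3) asks for "bleeding that occurs post-operatively requiring blood or blood product transfusion or an additional surgical procedure (and the relationship to SOC/PVS for RA/RV transection"; Protocol 4.7.5 (Visit 4) has the same item. At both visits it sits under a heading that confines it to bleeding from the renal artery or vein.

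On who judges and how:

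- SAP section 3 states: "This was an open-label study and therefore no blinding procedures were required".
- Protocol 5.1.3 has the principal investigator or a designee complete each eCRF and the investigator approve it.
- Protocol 9.1.5 makes the investigator responsible for the relationship of adverse events.
- SAP section 9 reports no data monitoring committee, and neither document describes adjudication of this endpoint.

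For adverse events, SAP 10.11 gives a rule: "Related events are those where the relationship is indicated as Possibly, Related, or Unknown". SAP 5.2 and 10.4 give no rule for the endpoint's own relationship field.

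**The concern.** A relatedness condition makes the endpoint the product of two things: how often a post-operative bleed needed intervention, and how often such a bleed was put down to the transection. Randomisation protects the comparison of the first. It does not protect the second when the person judging knows which stapler was used. If the share called related differs between arms, equal bleeding can look unequal, or a real difference can shrink or vanish.

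A condition tied to the device is reasonable for a device study. The difficulty is that the planned outputs do not let a reader see how many bleeding interventions the condition removed, or from which arm. The endpoint is one of the trial's two primary endpoints, and the primary objective covers post-operative as well as intra-operative interventions.

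**Working it through.** **The plan's own figures.** The documents give no event rate, margin or power for the safety endpoint. Their precision figure, at most 2.9%, belongs to the performance endpoint (6% of firings, 300 firings per group). It reproduces: 1.96 × √(0.06 × 0.94 / 300) = 2.69% by the Wald formula; the exact interval for 18/300 is 3.59% to 9.32%, a half-width of 2.86%. It says nothing about this endpoint.

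**Weight of one event.** Protocol 7.2 plans about 250 subjects, 1:1, so about 125 per arm. One reclassified subject moves an arm's rate by 1/125 = 0.8 points, two by 1.6 points. The exact two-sided 95% upper limit at n = 125 is 2.9% for 0 events, 4.4% for 1 and 6.9% for 3.

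**Effect of unequal attribution.** Let p be the proportion of subjects with any post-operative bleeding intervention and s the share classified as related. The endpoint estimates p × s in each arm, so the filtered difference is p(PVS) × s(PVS) − p(SOC) × s(SOC). All values of p and s below are assumptions chosen to show the mechanism.

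| p, SOC / PVS | s, SOC / PVS | Unfiltered difference | Filtered difference |
|---|---|---|---|
| 2% / 2% | 50% / 25% | 0 | −0.5 points |
| 4% / 4% | 50% / 25% | 0 | 2.0% to 1.0%: −1.0 points |
| 4% / 4% | 25% / 50% | 0 | 1.0% to 2.0%: +1.0 points |
| 6% / 6% | 50% / 25% | 0 | −1.5 points |
| 3% / 6% | 50% / 25% | +3.0 points | 1.5% to 1.5%: 0.0 points |
| 3% / 6% | 50% / 50% | +3.0 points | 1.5% to 3.0%: +1.5 points |

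The second and third rows show that the shift can go against either device. The last row shows that equal shares create no spurious difference but scale a real one down.

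**Precision of the unfiltered count.** At p = 4% in both arms the standard error of the difference is √(2 × 0.04 × 0.96 / 125) = 2.48 points. With half the events called related (2% per arm) it is √(2 × 0.02 × 0.98 / 125) = 1.77 points. The unfiltered row is therefore noisier, and shifts of the sizes shown for equal rates lie within sampling error. Its use is to show what was excluded, not to test a difference.

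**Do existing outputs fill the gap?**

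- Table 7 is filtered. It gives an interval per arm and has no difference row, although SAP 10.4 applies to this endpoint the same code that yields a difference.
- Table 4 reports transfusion among surgical characteristics, not as a post-operative bleeding outcome.
- Tables 12 to 18 count subjects by system organ class and preferred term, not by whether a bleed led to transfusion or surgery.
- Listings 15, 17 and 19 give case detail, not a comparison by arm.

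**Are the data there?** Protocol 3.3 lists post-operative surgical interventions unconnected with the transection, and transfusions. Visits 3 and 4 record concomitant procedures. Protocol 9.1.1 records all adverse events whatever their relationship, with the action taken. Against this, the Visit 3 and 4 bleeding item is headed for renal-vessel bleeding, those visits list no separate transfusion item, and the itemised transfusion field is intra-operative (Protocol 4.7.3.2). An all-bleeding count is probably recoverable from several forms, but the documents do not prove it.

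**The case against.** The strongest reply is that the endpoint matches the objective, which concerns bleeding from the transection. Bleeds elsewhere say little about the stapler and dilute the comparison. All adverse events are tabulated by arm without a relatedness condition, so a large imbalance in bleeding would probably show there. The 3% acceptance criterion applies to firings, so no pass or fail turns on this endpoint. All of this stands. It argues against replacing the endpoint and for modest weight. It does not supply the missing comparison.

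A reader might also infer more than the documents support:

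- *That Visits 3 and 4 capture every post-operative bleed, so the data are already in hand.* The phrase "and the relationship to SOC/PVS for RA/RV transection" may suggest this, but the heading above it limits the item to the renal vessels.
- *That a bleed of unknown relationship is device-related in Table 14 and a non-event in Table 7.* The levels Possibly, Related and Unknown belong to the adverse event scale in Protocol 9.1.5. Nothing says the endpoint's field uses them. The SAP is silent here rather than contradictory.
- *That the unfiltered count is free of open-label bias.* It removes the attribution step only; decisions to transfuse or re-operate are also made with the device known.
- *That bias would favour PVS, or that events will be few.* The documents give neither a direction nor an event rate.

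**Conclusion.** The point holds as a gap in the supportive analysis. The primary safety endpoint depends on an unblinded classification with no described adjudication and no stated rule for uncertain cases, and no planned summary lets a reader judge how far the classification shaped the result. The size of any bias cannot be derived; what can be stated is 0.8 points per reclassified event at 125 per arm.

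This rests on two inferences. The first is that the site makes the classification, which follows from Protocol 5.1.3 and 9.1.5 because no section assigns the task. The second is that no adjudication takes place under a document not available here. It is an inexpensive improvement worth making, not a flaw that invalidates the endpoint.

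**What to change.** 1. Keep the primary safety endpoint. Add to Table 7, on the Safety Set, a supportive row per arm for subjects with any post-operative bleeding that led to transfusion or a further surgical procedure, whatever relationship was recorded. Give the 95% confidence interval per arm and the PVS minus SOC difference, and read it beside the primary row.
2. Before programming, confirm eCRF coverage, because of the heading over the Visit 3 and 4 item. Build the count from the Visit 3 and 4 intervention and relationship fields, concomitant procedures and interventions, the Protocol 3.3 items on non-transection interventions and transfusion, and adverse event action taken. If coverage is incomplete, say so in a footnote.
3. In SAP 5.2 or 10.4, state how the endpoint's relationship field becomes yes or no, counting an uncertain or unknown relationship as related, in line with SAP 10.11 if the field has such levels. Use one wording of the condition across Protocol 7.6, SAP 5.2 and Table 7.

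The cost is some programming to combine forms, and higher, noisier rates because bleeds unrelated to the stapler enter the row. No new visit or assessment is needed if coverage is confirmed.

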# 8.0 RISKS AND BENEFITS OF THE STUDY DEVICE AND CLINICAL INVESTIGATION

The procedure being performed with powered vascular stapler is identical to the procedure subjects would receive as part of their standard of care procedure. To date, no risks have been reported beyond standard risks associated with simple laparoscopic nephrectomies and laparoscopic nephroureterectomies. This study may or may not provide any benefits to the subject.

# 9.0 ADVERSE EVENTS AND PRODUCT COMPLAINTS

# 9.1 **DEFINITIONS**

#### 9.1.1 Adverse Event

An adverse event is defined as any undesirable clinical occurrence in a subject that may or may not be attributable to the device or procedure. All AEs, regardless of their relationship to the procedure or device, are to be recorded in the eCRF and reported to the Sponsor.

In addition, the Investigator is required to provide:

- The onset and resolution dates of the event;
- The severity of the event;
- The outcome of the event;
- The relationship of the event to procedure and/or device (ECHELON FLEX™ Powered Vascular Stapler with Advanced Placement Tip or standard of care stapler); and
- The action taken for the medical management of the event.

Postoperative pain is expected and will not be documented as an adverse event unless the Investigator considers the pain to exceed what is typically anticipated following a laparoscopic nephrectomy or laparoscopic nephroureterectomy. (This data is separate from incisional and/or trocar pain).

# 9.1.2 Anticipated Adverse Events

An expected morbidity/procedural complication is defined as an AE that is known to be common or usual in nature, severity, or incidence during laparoscopic nephrectomies/ nephroureterectomies.

A list of anticipated AEs that may occur during this study are listed in Appendix I.

# 9.1.3 Serious Adverse Event

It is the Investigator's responsibility to determine if an AE is an SAE.

SAEs are AEs that:

- Led to death,
- Led to serious deterioration in the health of the subject, that either resulted in
  - a life-threatening illness or injury, or
  - a permanent impairment of a body structure or a body function, or
  - in-patient or prolonged hospitalization, or
  - medical or surgical intervention to prevent life-threatening illness or injury or permanent impairment to a body structure or a body function,
  - Led to fetal distress, fetal death or a congenital abnormality or birth defect

Note: "Death" should not be reported as an adverse event. The cause of death should be reported as an adverse event. The only exception is "Sudden Death" when the cause is unknown.

# 9.1.4 Severity of Adverse Events

It is the Investigator's responsibility to assess the severity of an AE. A change in severity may constitute a new reportable AE.

The following guideline should be used to determine the severity of each adverse event:

- **MILD:** Awareness of experience, but easily tolerated. No medical intervention required.
- **MODERATE:** Enough discomfort to interfere with usual activities. Medical intervention required.
- **SEVERE**: Inability to carry out usual activities. Medical intervention (including hospitalization or prolongation of hospitalization) required.

# 9.1.5 Relationship of Adverse Events

It is the Investigator's responsibility to assess the relationship of an AE to the study procedure (laparoscopic nephrectomies/ nephroureterectomies) and powered vascular stapler or SOC.

The following guidelines should be used in determining the relationship of an adverse event to the study device, study procedure, or other causality:

- Not Related A clinical event (including abnormal laboratory result) that results from causes extraneous to administration of device/procedure/other and is most likely due to alternative etiology, (i.e., pre-existing condition, underlying disease, intercurrent illness, concomitant medications);
- **Possibly** A clinical event (including abnormal laboratory result) that presents an unlikely association between device/procedure/other, which cannot be ruled out with certainty, but could also be explained by alternative etiology;
- Related- A clinical event (including abnormal laboratory result) that presents a

strong temporal relationship between device/procedure/other, in which an alternative etiology is unlikely; or

 Unknown – A clinical event (including abnormal laboratory result) that cannot be determined to be related or unrelated to device/procedure/other given the information obtained.

#### 9.1.6 **Product Complaints**

A product complaint is defined as any written, electronic or oral communication that alleges deficiencies related to the identity, labeling, quality, durability, reliability, safety, effectiveness, or performance of a device (i.e., stapler) after it is released for distribution (policy of Johnson and Johnson Medical Device Quality management). A product complaint may or may not be associated with an AE/SAE.

# 9.2 REPORTING PROCEDURES FOR ADVERSE EVENTS/PRODUCT COMPLAINTS

#### 9.2.1 Reporting Adverse Events

Data related to AEs will be recorded in the source documentation from the time of study enrollment (first incision) until the subject completes the study or terminates early. All AEs that are unresolved at study completion (or early termination) will be recorded as ongoing at study end.

Data related to SAEs will be collected until event resolution, or until the event is considered stable, or until all attempts to determine the resolution of the event are exhausted.

#### 9.2.2 Reporting Serious Adverse Events

The site must complete the SAE eCRF within 24 hours of becoming aware of the event.

Supporting SAE documentation can be faxed to:

The Investigator will also be required to assess if the SAE is considered anticipated (see Appendix I) and if the event involved a product complaint. The report of an SAE by a study site does not constitute an admission that study personnel or the user facility (hospital/clinic) caused or contributed to the event.

The study site is also responsible for submitting to the reviewing IRB/EC according to their IRB/EC procedures.

# 9.2.3 Reporting Product Complaints

All product complaints related to powered vascular stapler shall be documented throughout the clinical investigation.

Product complaints related to powered vascular stapler must be reported to the Sponsor in a timely manner and no later than 24 hours after becoming aware of the event. The Product Complaint Form must be emailed to the EES Customer Complaint team at the following email address:

One copy of the processed form should be kept on-site and the device should be retained. EES representatives will organize collection of the device for evaluation as needed.

